8.3.3. Physical Examination

Complete PEs will be performed at screening, the Final Study Visit (Day 51) and early withdrawal, if applicable. The following will be examined: cardiovascular system (including a standard 12-lead electrocardiogram at screening only, to be read at the site); lymphatic/hematological, respiratory system; nervous system; skin and appendages; abdominal/gastrointestinal system; metabolic/endocrine, musculoskeletal system; and ear, nose, and throat.

Symptom-directed PEs will be performed at all visits except the Screening, Final Study Visits and early withdrawal (including any unscheduled visits), only if required (ie, in response to the report/collection of AEs/SAEs/potential AESIs).

Abnormal PE findings are to be recorded as AEs if new or changed in severity any time after the first administration of any IP and PE AEs should be assessed for severity and causality. Grade 3 (or higher) PE findings could trigger individual or study halting rules if considered associated with IP administration (see [Section 7](#)). Physical examination abnormalities are not separately reported as AEs if the PE abnormality is part of a symptom complex that is already reported as an AE.

8.3.4. Vital Signs

Vital signs including seated/semi-recumbent systolic and diastolic blood pressure, heart rate, respiration rate, and temperature will be obtained at Screening and each subsequent clinic visit through Day 51/EWV (except at AM and PM clinic visits for groups 1A and 2A, and at Day 37 for all groups), including unscheduled visits. Height and weight will only be recorded at Screening. On vaccination days (Days 8 and 23), vital signs will be assessed prior to vaccination and at 30 ± 5 minutes post-vaccination.

All vital sign abnormalities determined by the PI or designee to be a clinically significant change from baseline for that participant should be recorded as AEs. Grade 3 or higher vital signs will be repeated twice to verify that the severity is a Grade 3 or higher. If two of the three assessments are Grade 3 or higher, the vital sign should be reported as a Grade 3 or higher abnormality. Vital sign abnormalities may trigger individual participant or study halting rules (refer to [Section 7](#)).

8.3.5. Other Safety Assessments

8.3.5.1. E-diary Records

Participants will be asked to fill out an electronic diary (e-diary) daily for for postvaccination reatogenicity events (all groups) and an e-diary for antibiotic compliance (Groups 1 and 2). Participants who do not have or don't want to use their personal electronics to access the web-enabled e-diary will be provided a hand-held device for purposes of this study. Participants will receive instructions on reatogenicity and/or antibiotic compliance e-diary completion. Participants will be asked to complete the reatogenicity e-diary at the same time each day to capture observations on the previous 24-hour period. Staff at the clinical site will follow up participant's reatogenicity and/or antibiotic e-diary noncompliance.

AV7909 Anthrax Vaccine

IND 014451

Protocol EBS.AVA.210, Version 3.0 (28 October 2019)

There are separate e-diary requirements for this study depending on the treatment group assignment:

- Participants in all three groups will be required to fill out an e-diary to capture reactogenicity events after each vaccination. All participants will receive an injection site reaction measuring tool and an oral thermometer to support in completing the reactogenicity e-diary.
- Participants in Group 1 and Group 2 will be required to also fill out a separate e-diary to capture antibiotic compliance.

The e-diary to capture reactogenicity events postvaccination will collect the following information:

- each participant's daily oral temperature at the same time each day
- local injection site and systemic reactogenicity events
- whether they have used any pain medications (eg, acetaminophen, aspirin, ibuprofen)

Reactogenicity (solicited systemic and local injection site reactions) will be monitored by the site for at least 30 minutes after vaccination with special attention being paid to signs and symptom of immediate hypersensitivity responses (eg, anaphylaxis, bronchospasm, urticaria, angioedema). Thereafter, local injection site and systemic reactogenicity responses will be assessed daily by participants in their e-diaries for at least seven days following each vaccination. Information will be solicited on the following local injection site reactogenicity reactions: warmth, tenderness, itching, pain, arm motion limitation, redness, lump, swelling, and bruising. In addition, information will be solicited on the following systemic reactogenicity reactions: tiredness/fatigue, muscle ache, headache, and fever (oral temperature). Except for oral temperature, swelling, and redness, the participant will be prompted to grade each reaction according to the grading scale provided below.

- Grade 0 (Absent): Symptom not present
- Grade 1 (Mild): Symptom present but does not interfere with activities of daily living
- Grade 2 (Moderate): Symptom causes some interference with activities of daily living
- Grade 3 (Severe): Symptom prevents activities of daily living or requires medical intervention

Participants will also be asked to respond (yes/no) if they have taken pain/fever medications such as acetaminophen, aspirin, and nonsteroidal anti-inflammatory drugs (NSAIDs; eg, ibuprofen) or other medication in the past 24 hours. Participants will be directed to not take these types of medications 24 hours before or after vaccinations (refer to [Table 3](#)). Investigational site staff will review participant e-diary entries on a routine basis to assess compliance, need for re-instruction and evaluation against individual participant and study halting rules. These reviews will also occur on Day 23 (1 ±d) and Day 37 (1 ±d).

For the assessment of severity of swelling and redness, participants will use the injection site reaction measurement tool to measure redness and swelling at the injection site and then grade these accordingly. The redness grade will be based on greater of the two perpendicular

AV7909 Anthrax Vaccine

IND 014451

Protocol EBS.AVA.210, Version 3.0 (28 October 2019)

measurements in centimeters, while swelling grade will be based on greater of the two perpendicular measurements in centimeters and the functional scale (if applicable); see [Table 12](#).

Investigator sites will be notified of any Grade 3 or higher severity scores for follow-up and/or further assessment of symptoms. The site will record verified Grade 3 or higher e-diary reactions as an AE into the AE eCRF. If these reactions start out as mild in severity on a given day, the start date should be recorded as the first date that the reaction is noted as mild in severity. If these reactions end as mild in severity on a given day, the end date should be recorded as the last date that the reaction is noted to be mild in severity. The AE severity will be recorded as the highest severity score within the start and stop dates. If severe reactions reappear in the e-diary after they were absent for one or more days, a second AE will be recorded on the AE eCRF. During follow-up visit(s), the investigator will query the participant about all ongoing e-diary AEs and document the start and stop date of any Grade 3 or higher AEs on the AE page in the eCRF.

If local injection site or systemic reactions continue beyond seven days, participants will be prompted to continue e-diary entries until they are symptom-free for two consecutive days. For any type of reactogenicity persisting two weeks or more, the PI or designee will evaluate the reaction at the next scheduled visit and/or determine based on the nature and severity if a more immediate unscheduled follow-up visit is required to fully assess the reaction. Investigational sites will be alerted of any Grade 3 or higher (eg, ER visit or hospitalization) solicited systemic reactions, which will require discontinuation of vaccinations upon verification by the PI or designee of the Grade 3 or higher status. The PI or designee may require participants reporting Grade 3 or higher reactions to return to the clinic for an unscheduled visit to aid in this evaluation.

In addition to any reaction considered an AE by the PI, solicited reactions reported in the e-diary will be recorded by the PI or designee on the AE eCRF if they are serious (ie, a solicited reaction will be considered ‘serious’ if confirmed by the investigator to be a Grade 4, or a Grade 3 that upon the investigator’s assessment meets any of the SAE criteria outlined in [Section 9.1.2](#)); result in discontinuation of study product or withdrawal from the study; or remain unresolved for 14 days or more. Solicited systemic reactions may require discontinuation of vaccinations based on individual participant halting rules (see [Section 7.3](#)).

The rating scale to be used for reactogenicity events is the same toxicity grading scale provided in [Appendix A](#), the FDA Guidance for Industry: *Toxicity Grading Scale for Healthy Adult and Adolescent Volunteers Enrolled in Preventive Vaccine Clinical Trials* {[CBER, 2007](#)}, where symptoms are assessed as Grade 1=mild through Grade 4=potentially life-threatening. Additionally, a Grade of 0 will be available in the e-diary in order to allow the participant to record “symptom not present.” For most of the reactogenicity events, there is a direct corresponding symptom entry in the toxicity grading scale (eg, for systemic reactions: fever, headache, fatigue, myalgia; for local reactions: pain, tenderness, erythema/redness, induration/swelling) – refer to [Table 12](#).

For reactogenicity events with no direct corresponding symptom entry in [Table 12](#) (eg, warmth, itching, arm motion limitation, bruising), the grading for “illness or clinical AE” will be used to rate the symptom severity. The symptom-severity descriptions in [Table 12](#) will be translated to lay language in the e-diary instrument to promote participant understanding.

AV7909 Anthrax Vaccine

IND 014451

Protocol EBS.AVA.210, Version 3.0 (28 October 2019)

Participants in Groups 1 and 2 will be required to complete e-diary entries to capture their compliance to their antibiotic doses of ciprofloxacin or doxycycline respectively. Participants in these groups will begin e-diary entries as soon as they receive their first dose of antibiotic. The e-diary will remind them to self-administer their antibiotic (ciprofloxacin or doxycycline) at appropriate times and record those times in the e-diary. For those participants receiving an antibiotic, the investigational site staff will review e-diary entries with the participant at every visit overlapping with the antibiotic courses.

8.4. Pharmacokinetics Sessions and Trough Concentrations of Antibiotics

For the participants randomized to Groups 1A or 2A, antibiotic serum concentrations will be measured, and PK parameters will be assessed.

8.4.1. Ciprofloxacin

On days with PK sessions (Days 4, 8, 31 and 35), blood samples for measurement of ciprofloxacin concentrations will be collected at 0.25, 0.5, 0.75, 1, 1.5, 2, 2.5, 3, 4, 5, 6, 8, 10 and 12 hours post dose (± 5 min through hr 4, then ± 15 min thereafter).

Blood samples for determination of ciprofloxacin pre-dose or trough concentrations will be collected on Days 4, 5, 6, 7 and 8 and on 31, 32, 33, 34 and 35 prior to administration of the morning ciprofloxacin dose.

8.4.2. Doxycycline

On days with PK sessions (Days 2, 8, 32 and 38), blood samples for measurement of doxycycline concentrations will be collected at 0.25, 0.5, 0.75, 1, 1.5, 2, 2.5, 3, 4, 5, 6, 8, 10 and 12 hours post dose (± 5 min through hr 4, then ± 15 min thereafter).

Blood samples for determination of doxycycline pre-dose or trough concentrations will be collected on Days 2, 3, 4, 5, 6, 7 and 8 and on 32, 33, 34, 35, 36, 37 and 38 prior to administration of the morning doxycycline dose.

8.4.3. Specimen Collection, Preparation, Handling, and Shipping

Instructions for the collection, preparation, handling, storage, and shipment of the study samples will be provided in study-specific laboratory manuals.

8.5. Data Safety Monitoring Board

Independent safety oversight will be provided by a DSMB which will be notified of significant AEs (eg, SAEs, severe AEs recorded on the eCRF, potential AESIs of autoimmune etiology, or any other events the medical monitor deems medically relevant) as determined by the medical monitor on an ongoing basis, including any that result in study halt based on prespecified stopping rules (refer to [Section 7.1](#)). The DSMB will consist of at least three voting members, one of whom will be an expert in rheumatology/immunology to specifically support the evaluation of potential AEs for autoimmune etiology. The DSMB will make recommendations regarding the safety of continuing enrollment and dosing. Study enrollment and dosing may be

AV7909 Anthrax Vaccine

IND 014451

Protocol EBS.AVA.210, Version 3.0 (28 October 2019)

interrupted at the request of the DSMB Chair if it is believed that an AE represents a significant safety concern pending full DSMB evaluation.

The DSMB Chair will receive and evaluate each SAE, each severe AE (reported on the AE eCRF), and potential AEs of autoimmune etiology. The DSMB Chair will determine if an *ad hoc* review by the entire DSMB is necessary. An *ad hoc* review by the entire DSMB, when it occurs, may be focused on a single participant or on data for all participants. The operations of the DSMB will be detailed in a DSMB Charter to be finalized prior to screening of the first participant.

At least one DSMB member will be an expert in autoimmune disorders (eg, rheumatologist, immunologist). This member will review all potential AESIs to assess cases for autoimmune etiology, if preexisting or new onset, and relationship to the IP. Details on the recording of assessment outcomes will be detailed in the DSMB Charter.

9. REPORTING ADVERSE EVENTS

9.1. Definitions

9.1.1. Adverse Event

An AE is any untoward medical occurrence in a participant administered an investigational product regardless of its causal relationship to the study treatment. An AE can therefore be any unfavorable and unintended sign (including an abnormal laboratory finding, for example), symptom, or disease temporally associated with the use of a medicinal product, whether or not considered related to the medicinal product.

9.1.2. Serious Adverse Event

A serious AE (SAE) is any untoward medical occurrence at any dose that fulfils one or more of the following:

- Results in death
- Is life-threatening, ie, the participant was, in the opinion of the investigator, at immediate risk of death from the event as it occurred (does not include an event that, had it occurred in a more severe form, might have caused death)
- Requires inpatient hospitalization or prolongation of existing hospitalization. (Note: a prescheduled hospitalization is not considered an SAE.)
- Results in persistent or significant disability or incapacity
- Is a congenital anomaly or birth defect
- Is another medically significant event that, based upon appropriate medical judgment, may jeopardize the participant and may require medical or surgical intervention to prevent one of the outcomes listed above (eg, allergic bronchospasm requiring intensive treatment in an emergency room or home, blood dyscrasias or convulsions that do not result in hospitalization, the development of drug dependency or drug abuse)

9.1.3. Adverse Events of Special Interest

For this trial, AESIs are defined as any AE having an autoimmune etiology. [Appendix B](#) provides a list of AESI terms defined by FDA's CBER as potentially associated with autoimmune disease that might represent a safety signal for vaccine-associated autoimmunity. Monitoring for late-onset AESIs, ie, those reported after the final visit on Day 51, will extend through 12 months following the last vaccination. Potential AESIs will be evaluated by a member of the DSMB having expertise in this area (refer to [Section 8.5](#)). Once assessed as autoimmune in nature, the event will be considered as a confirmed AESI.

9.2. Eliciting and Reporting Adverse Events

AEs (including SAEs and potential AESIs) reported spontaneously by the participant and/or in response to an open question from the PI or designee or revealed by observation (eg, during PE

AV7909 Anthrax Vaccine

IND 014451

Protocol EBS.AVA.210, Version 3.0 (28 October 2019)

or from a clinical test result) will be recorded on the AE eCRF if they occurred from the time of the first administration of any IP (Day 2 for Group 2, Day 4 for Groups 1 or Day 8 for Group 3) through Day 51 or EWV, regardless of causal association with the IP. AE reporting is required for any new observation presenting after the first receipt of any IP or for a deterioration of baseline condition (eg, increased severity/frequency). From the signing of the ICF until immediately before the administration of their first IP, only AEs resulting from a study-related procedure will be recorded on the AE eCRF; all other events reported in these time periods will be recorded as signs and symptoms on the Medical History eCRF. If there is any doubt as to whether a clinical or laboratory observation is an AE, the event will be considered an AE and recorded on the AE eCRF. After Day 51 and through the 12-month safety follow-up, AEs, SAEs (meeting definition per [Section 9.1.2](#)) and AEs assessed by the DSMB to be of autoimmune etiology (refer to [Section 8.5](#)), ie, AESIs, will be recorded on the AE eCRF.

Refer to the specific sections on clinical laboratory tests ([Section 8.3.2](#)), PEs ([Section 8.3.3](#)), vital signs ([Section 8.3.4](#)), and e-diary reactogenicity ([Section 8.3.5.1](#)) for details on AE reporting based on participant observation and clinical test results.

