All participants who have received at least one vaccination will be encouraged to continue with the scheduled study safety evaluations, including any remaining study visits (safety assessments only), collection of samples for TSH and autoantibodies (only if medically indicated) and the safety follow-up calls. Participants who decline will be encouraged to complete the EWV (see Section 8.1.8) and followed for safety through the 12-Month (Day 388 ± 14d) Safety Follow-up phone call. If the discontinuation was due to an AE, participants will be followed until the event has resolved or stabilized or the participant has been referred to an outside physician.

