8.1.7. Quarterly Safety Follow-up Phone Calls

Following the last scheduled vaccination, the site will conduct quarterly safety follow-ups in which participants are contacted by phone at 3 months (Day 114 ± 14 d), 6 months (Day 205 ± 14 d), 9 months (Day 296 ± 14 d) and 12 months (Day 388 ± 14 d). These phone contacts will be scheduled to key off the participant's actual or, if missed, target Day 23 visit (intended last vaccination day) so that all participants (even those failing to receive both vaccinations but who are followed for safety only) are contacted 3 months after their target Day 23.

The following assessments will be performed over the phone at the 3 months (Day 114 ± 14 d), 6 months (Day 205 ± 14 d), 9 months (Day 296 ± 14 d) and 12 months (Day 388 ± 14 d) contacts:

- Assess and document, AEs, SAEs and potential AESIs (refer to [Section 9.3](#))
- For WOCBP, confirm continued use of an adequate method of contraception and inquire about any possible pregnancies (refer to [Section 9.4](#))
- If an AE, SAE and/or an AESI is reported, record any associated medications
- Review the status of ongoing AEs/SAEs/AESIs to update the resolution status

During the telephone calls, the staff member is to inquire about and record in source documentation any AEs and SAEs occurring since either the Day 51 visit or the previous phone contact. Any occurrence of SAEs will be reported to Emergent immediately as specified under [Section 9.3](#) and followed up per procedures described in [Section 9.7.2](#). If an SAE has occurred, it will be recorded on the AE eCRF with any medications taken also recorded on the appropriate eCRF.

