8.1.8. Early Withdrawal Visit

Any participant who withdraws early or is discontinued for any reason will be asked to complete an EWV.

1. For participants in Groups 1 and 2, review the participant's remaining antibiotic supply and count the number of remaining doses to document compliance; record total remaining in source document.
2. Perform complete physical examination.
3. Assess vital signs (seated/semi-recumbent blood pressure, heart rate, respiratory rate and temperature).
4. For WOCBP, collect and perform serum pregnancy test.
5. If EWV occurs within the visit window for Day 37, collect blood sample for TNA.
6. Collect blood sample for hematology.
7. Collect blood sample for serum chemistry.
8. Collect urine sample for urinalysis.
9. For participants who have received at least one vaccination, collect blood sample for TSH & autoantibody determination.
10. Review entries in e-diary with participant.
11. Review and record AEs.
12. Record concomitant medications.

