### 2.2.4 Safety Assessments

#### 2.2.4.1 Adverse Events

AEs (including SAEs and potential AESIs) will be recorded on the AE eCRF if they occurred from the time of the first administration of any study treatment (Day 2 for Group 2, Day 4 for Groups 1 or Day 8 for Group 3) through Day 51 or EWV. From the signing of the ICF until immediately before the administration of their first study treatment, only AEs resulting from a study-related procedure will be recorded on the AE eCRF. After Day 51 and through the 12-month safety follow-up, AEs, SAEs and AEs assessed by the DSMB to be of autoimmune etiology, i.e., AESIs, will be recorded on the AE eCRF.

Safety follow-up phone contacts to collect information on AEs, SAEs and AESIs will occur at 3 months (Day 114  $\pm 14$  days), 6 months (Day 205  $\pm 14$  days), 9 months (Day 296  $\pm 14$  days), and 12 months (Day 388  $\pm 14$  days) after the last scheduled vaccination.

Refer to Protocol EBS.AVA.210, [Section 9.2](#) for reporting adverse events.

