### 3.4 Analysis Time Points

Participant visits occur on protocol-specified days with associated visit windows. The schedule may shift by  $\pm 1$  day at the following visits:

- Day 23 visit of the second vaccination for all participants.
- Day 37 visit of TNA assessment for Group 1, 2B, and 3. There is no shifting flexibility for Group 2A at this visit as PK assessment schedule at Day 38.
- Day 51 of final study visit for all participants.

If not otherwise specified, for the purposes of analysis, the analysis visits will be assigned as provided in **Table 2** for vaccination, immunogenicity (TNA) testing, clinical laboratory data,

vital signs, and physical examinations. Data at unscheduled visits will not be presented in the by-visit summary analyses but will be included in the summary tables by maximum toxicity grade or abnormality when applicable, and in data listings.

**Table 2 Analysis Windows for Vaccination, Immunogenicity (TNA) Testing, Clinical Laboratory Data, Vital Signs, and Physical Examinations**

Analysis Visit	Nominal Day	Lower Limit of Study Day	Upper Limit of Study Day
Baseline	NA	-28	Prior to the first exposure to any study treatment
Day 1	1	1	1
Day 8	8	8	8
Day 23	23	22	24
Day 37	37	36 for Group 1, 2B, and 3, 37 for Group 2A	38 for Group 1, 2B, and 3, 37 for Group 2A
Day 51	51	50	52

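### Adverse events with onset between an early withdrawal visit and Day 51 fall in neither AE recording window, although the AE endpoint runs to Day 51

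*Protocol*

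**What the plan says.** Protocol Section 9.2 defines two periods for entering events on the AE eCRF. The first starts at first investigational product and is given as "Day 2 for Group 2, Day 4 for Groups 1 or Day 8 for Group 3) through Day 51 or EWV". The second begins "After Day 51 and through the 12-month safety follow-up, AEs, SAEs" and adds events that the DSMB judges autoimmune. SAP 2.2.4.1 carries the same two periods, the second in nearly identical words: "After Day 51 and through the 12-month safety follow-up, AEs, SAEs and AEs assessed by the DSMB".

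Section 8.1.7 tells call staff to ask about "any AEs and SAEs occurring since either the Day 51 visit or the previous phone contact". The calls explicitly include participants who missed a vaccination and are followed for safety only.

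Sections differ on who has an EWV:

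- Section 8.1.8: "Any participant who withdraws early or is discontinued for any reason will be asked to complete an EWV".
- Section 7.3.1: vaccinated participants who stop treatment are first asked to keep their remaining visits. Then "Participants who decline will be encouraged to complete the EWV", and those participants are still followed to the 12-month call. Section 7.3.2 is similar on who is offered an EWV.
- Section 7.3: vaccinated participants who stop treatment are encouraged to continue visits and calls, with no mention of an EWV. Participants in Groups 1 and 2 who stop before the first vaccination are asked back for the early withdrawal procedures.

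The endpoints (Protocol 3.2.2 and 10.1.2.1, SAP 2.3.2.1) run from first product to Day 51 for AEs, and to 12 months for SAEs and AESIs. None is cut at an EWV.

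**The concern.** The first window closes at whichever of Day 51 or the EWV applies, but the second opens only after Day 51. For someone whose EWV comes earlier, the two do not meet. The call script does not bridge them: at the 3-month call this participant has had neither a Day 51 visit nor an earlier call, so the look-back has no defined start.

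The recording rule is therefore narrower than the secondary AE endpoint it feeds. The participant stays in the Safety Population denominator, while part of the period the endpoint covers has no instruction to record. The information is obtainable, because the plan keeps this person in telephone follow-up. The uncovered time can include most of the weeks after the first vaccination, in people who stopped early.

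**Working it through.** The plan gives no figure to reproduce here; the check compares interval limits.

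**Inputs**

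- Start of first window: Day 2 (Group 2), Day 4 (Group 1), Day 8 (Group 3), from Section 9.2.
- End of first window: Day 51 or the EWV (Section 9.2). Section 9.2.3 and the schedule footnotes use the same cut-off.
- Start of second window: after Day 51 (Section 9.2, SAP 2.2.4.1).
- First call: Day 114 ± 14, that is Day 100 to Day 128 (Section 8.1.7).

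**Length of the gap.** Uncovered days = 51 − EWV day.

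| EWV day | Uncovered days |
|---|---|
| 8 (just after vaccination 1) | 51 − 8 = 43 |
| 10 | 51 − 10 = 41 |
| 23 | 51 − 23 = 28 |
| 37 | 51 − 37 = 14 |

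**Share of the AE endpoint period, EWV on Day 10.** Full period = 51 − start day + 1. Covered = 10 − start day + 1.

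| Group | Full period | Covered | Uncovered |
|---|---|---|---|
| 2 (from Day 2) | 50 | 9 | 41 |
| 1 (from Day 4) | 48 | 7 | 41 |
| 3 (from Day 8) | 44 | 3 | 41 |

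**Who is exposed.** Three conditions must hold together: at least one vaccination received, an EWV before Day 51, and continued telephone follow-up. Participants in Groups 1 and 2 who were never vaccinated leave long-term follow-up by design (Section 6.1.4). Those who withdraw consent or are lost supply no later data under any wording.

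**Dependence on the EWV rule.** Under Sections 7.3.1 and 7.3.2, the vaccinated participants exposed are those who decline further visits. If the word discontinued in Section 8.1.8 covers stopping treatment, someone could have an EWV, go on attending visits, and already have the first window formally closed. The text does not say which is meant.

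**Analysis stage.** SAP 8.1.1 counts any event starting on or after first exposure as treatment-emergent, with no end date, and SAP 8.1.2 summarises both to Day 51 and to 12 months. An event in the gap would be counted if recorded, so the gap lies in the recording instruction.

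**The case against.** The best counter-argument comes from Section 9.2 itself: "AE reporting is required for any new observation presenting after the first receipt of any IP". That sentence has no end date. Section 9.7.1 also treats Day 51 and the EWV as one closing milestone, so the phrase about the period after Day 51 could be shorthand for the telephone phase. The task list in Section 8.1.7 asks staff to document AEs, SAEs and potential AESIs without a start point. A careful site could record everything. This stands as a possible reading, but it competes with two explicit windows and a specific look-back, and the SAP repeats the windows without settling the matter.

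Several stronger inferences are tempting and are not supported.

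- *That SAEs and AESIs are lost.* Section 9.3.1 requires both to be reported within 24 hours of awareness, whether or not an EWV has taken place. Section 9.7.2 expects the information on the report form and the AE eCRF, and call staff elicit possible autoimmune events with no look-back limit. What remains for these events is unclear wording on the eCRF windows.
- *That a long gap is the usual course after stopping treatment.* Sections 7.3 and 7.3.1 make continued visits the default, and an AE that caused the stop is followed until it resolves, stabilises or is referred.
- *That the antibiotic groups lose more.* Table 4 item 1 gives them additional reasons to stop treatment. Stopping treatment does not end visits, so a difference in ascertainment does not follow.
- *That EWV laboratory results drop out.* SAP Table 2 has no EWV row, and SAP 3.4 says "Data at unscheduled visits will not be presented in the by-visit summary analyses". That sentence concerns unscheduled visits and still keeps them in maximum-grade tables and listings. The highest-grade laboratory table in SAP 8.2 is not tied to the Day 51 row. Placing an early EWV sample in that row would mix time points.

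**Conclusion.** The concern holds in a limited form. For a vaccinated participant who declines the remaining visits, has an EWV before Day 51 and stays in telephone follow-up, the recording windows leave 51 minus the EWV day uncovered, although the AE endpoint runs to Day 51. The loss is mainly of non-serious adverse events.

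The documents give no rate of early EWVs. The number affected is probably small, since it requires declining visits while accepting calls. The planning allowance of up to 25% per group in Protocol 10.2 should not be read as an EWV rate: the synopsis describes it as exclusion from the immunogenicity population.

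No hypothesis test, sample size or power figure is touched; safety is descriptive. The conclusion rests on taking the two windows in Section 9.2 as operative over the open-ended sentence beside them. Because a site could reasonably do either, recording could differ between sites, which is reason enough to settle the wording.

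**What to change.** 1. In Section 9.2 and SAP 2.2.4.1, make recording continuous by starting the second window after Day 51 or the EWV, whichever is earlier. State that the AE endpoint runs to Day 51 whether or not an EWV took place. Align Section 9.2.3 and the schedule footnotes.
2. In Section 8.1.7, have the calls ask about events since the last visit or contact, including an EWV.
3. Reconcile Section 8.1.8 with Sections 7.3, 7.3.1 and 7.3.2 so that one rule says who has an EWV and whether discontinued refers to treatment or to the study. Keep the existing EWV provision for never-vaccinated participants in Groups 1 and 2.

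These are wording changes, with no added visits or samples. The cost is longer recall at the first call for a few participants. For an EWV on Day 10 and a call on Day 114, the look-back is 114 − 10 = 104 days, against 114 − 51 = 63 for someone seen on Day 51. The extra 41 days are the gap itself.
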